### Hypothesis or Research Question

- Hypothesis 1: Laboring women who receive epidural analgesia and elevate their legs on a peanut ball will experience a lower incidence of requiring intervention for low blood pressure compared to laboring women who receive epidural analgesia and do not elevate their legs.
- Hypothesis 2: Laboring women who receive epidural analgesia and elevate their legs on a peanut ball will experience a lower incidence of hypotension compared to laboring women who receive epidural analgesia and do not elevate their legs.  
\*hypotension is defined as SBP < 90 mmHg or an SBP decreases more than 20% from baseline
- Hypothesis 3: Infants of laboring women who receive epidural analgesia and elevate their legs on a peanut ball will experience a lower incidence of late or prolonged decelerations compared to laboring women who receive epidural analgesia and do not elevate their legs.

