## Research Plan

- **Study Design**

This study will use a randomized, non-blinded, controlled design with two arms:

- Arm 1 (Intervention): Immediately after epidural placement, patient will be placed in a left tilt position with her hip on a wedge and both of her legs elevated on an orange peanut ball. She will remain in this position for approximately 40 minutes.
- Arm 2 (Control/Standard Care): Immediately after epidural placement, patient will be placed in a left tilt position with her hip on a wedge. She will remain in this position for approximately 40 minutes.

- **Setting for the study**

The study will take place on Good Samaritan Hospital's Labor and Delivery Unit. This unit consists of 20 labor rooms and provides care to approximately 11 laboring women each day.

- **Participants**

The study will enroll 300 women who meet the following inclusion/exclusion criteria:

Inclusion Criteria:

- Laboring at Good Samaritan Hospital Labor & Delivery Unit
- 37+ weeks gestation
- Planned vaginal delivery
- Planned epidural analgesia

Exclusion Criteria:

- Under 18 years old
- Does not speak English
- Unable to consent to involvement in the research study
- Attended less than 3 prenatal care office visits
- Diagnosed with fetal demise
- Diagnosed with fetal anomalies
- Contraindications to both legs being elevated (ex: fractured bones, lower limb amputation, etc.)
- Contraindications to receiving 1L of IV fluids
- Requiring IV hypertensive medications
- Requiring IV magnesium

Sample Size Determination: A power analysis was conducted using a dichotomous outcome variable, requiring intervention for low blood pressure, with an expected difference [(33% incidence rate (Auroy et al., 1997), clinical significance would be a decrease to 15%)] (0.2), power of 0.8, and level of significance 0.05. It was determined that 120 patients would be needed in each group, for a total sample size of 240 patients. To allow us to also examine the impact on occurrence of infant decelerations and to allow for the possibility of removing participants from the final analysis due to missing data, we plan to enroll 300 patients (150 in each group).

- **Data Collection**

Before the study begins, information about the study will be provided to the nurses on the L&D unit including education about the study purpose, inclusion/exclusion criteria, and procedures.

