When a patient who meets the inclusion/exclusion criteria is admitted, a nurse will describe the study, answer any questions the patient has, and if the patient wants to enroll in the study, the study team nurse will review the information consent form. After the patient provides written informed consent, the nurse will remove the next envelope out of a box of prefilled and sealed opaque envelopes. The envelope will provide the Subject ID number to be used on all study-related documentation and the study Arm that the patient has been randomized to, either:

1. Leg Elevation Group
2. Standard Care Group

These envelopes will be filled using a computerized simple random number generator (1:1 randomization) prior to the start of the study.

In addition to the group assignment, the envelope will include a data collection form. Data will be recorded directly on this form during the patient's visit. The form will collect the following information:

- Whether patient was assigned to the leg elevation group or the standard care group
- Patient age
- Pregnancy history
- Height
- Weight
- Whether pregnancy is a singleton or multiple pregnancy
- Blood pressure documented at last prenatal office visit
- Threshold systolic blood pressure (20% decrease from office visit blood pressure) – The study team nurse will calculate threshold systolic blood pressure by calculating the systolic blood pressure from most recent office visit multiplied by 0.8
- Time of epidural placement
- Time legs elevated on peanut ball (Intervention group only)
- Time legs removed from peanut ball (Intervention group only)
- Did the infant have any late or prolonged decelerations within the 1 hour after epidural placement? Yes/No
- Did the RN have to perform any interventions to address prolonged or late decelerations during the 1 hour after epidural placement? Yes/No
- Did the anesthesia provider treat the maternal blood pressure during the 1 hour after epidural placement? Yes/No

RN will complete the data collection form and place the signed informed consent form and data collection form in a locked room designated for study materials.

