Hypothesis 1: Laboring women who receive epidural analgesia and elevate their legs on a peanut ball will experience a lower incidence of requiring intervention for low blood pressure compared to laboring women who receive epidural analgesia and do not elevate their legs.

*To compare the effects of leg elevation, a Chi Square test will be used to compare occurrence of receiving intervention for low blood pressure for patients who elevated their legs to patients who did not elevate their legs. A level of significance of  $\alpha=0.05$  will be used.*

Hypothesis 2: Laboring women who receive epidural analgesia and elevate their legs on a peanut ball will experience a lower incidence of hypotension compared to laboring women who receive epidural analgesia and do not elevate their legs.

*To compare the effects of leg elevation, a Chi Square test will be used to compare occurrence of maternal hypotension for patients who elevated their legs to*

*patients who did not elevate their legs. A level of significance of  $\alpha=0.05$  will be used.*

Hypothesis 3: Infants of laboring women who receive epidural analgesia and elevate their legs on a peanut ball will experience a lower incidence of late or prolonged decelerations compared to laboring women who receive epidural analgesia and do not elevate their legs.

*To compare the effects of leg elevation, a Chi Square test will be used to compare occurrence of late or prolonged infant decelerations for patients who elevated their legs to patients who did not elevate their legs. A level of significance of  $\alpha=0.05$  will be used.*

Interim data analysis will occur (1) once approximately 1/3 of the participants have been enrolled and (2) once approximately 2/3 of the participants have been enrolled. If interim calculations at time (1) or time (2) note a significant difference between groups in maternal hypotension or frequency of late or prolonged fetal decelerations, data collection will be completed at that time and final analysis will be completed.

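### Early stopping on any 0.05-level difference in hypotension or decelerations, with no interim boundary, roughly doubles the chance of a false claim on those outcomes and can cut the sample for the only powered outcome

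*Combined protocol and SAP*

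**What the plan says.** The Statistical Analysis section gives each of the three hypotheses a chi-square test at 0.05. For H1, "a Chi Square test will be used to compare occurrence of receiving intervention for low blood pressure"; H2 concerns maternal hypotension and H3 late or prolonged decelerations.

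It then schedules two looks: "Interim data analysis will occur (1) once approximately 1/3 of the participants have been enrolled", and again at about two thirds. Data collection ends, and the final analysis follows, if either look should "note a significant difference between groups in maternal hypotension or frequency of late or prolonged fetal decelerations, data collection will be completed". H1 does not trigger the rule. No interim level, alpha spending, division between the two triggering outcomes or reduced final level is given.

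Sample Size Determination rests on H1 alone: "A power analysis was conducted using a dichotomous outcome variable, requiring intervention for low blood pressure", with 33% against 15%, "power of 0.8, and level of significance 0.05". It arrives at 120 per group and plans to enrol 300, 150 per group.

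The Results report 104 consented, 102 randomized and 92 analysed (54 and 38). They do not mention an interim look or a reason for ending enrolment.

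**The concern.** If significant means p<0.05, as it does everywhere else in the plan, H2 and H3 each get three chances to cross the same line, and either one ends the trial. A stop for H2 or H3 also fixes the sample for H1 at about 50 or 100 per arm, although H1 is the outcome the trial was sized for. At stake are the error rate behind any H2 or H3 claim and the power for H1.

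The Results raise a related question of disclosure. Enrolment ended at 102/300 = 34% randomized, close to the first planned look, without explanation.

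**Working it through.** **Inputs from the documents.** Level 0.05; chi-square tests (hence two-sided, no continuity correction stated); looks at 1/3, 2/3 and the end of 300; 1:1 allocation; H1 rates 33% and 15%.

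**Assumptions.** Looks at exactly 50, 100 and 150 per arm. The correlation between outcomes is not given, so ranges are shown. H2 and H3 effects are not given, so four scenarios are shown.

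**Step 1: the plan's own sample size.** With mean rate 0.24,

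n = [1.96·√(2·0.24·0.76) + 0.842·√(0.33·0.67 + 0.15·0.85)]² / 0.18² = 87.2, so 88 per arm.

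The stated 120 is not reproduced. At 120 per arm the power is 91%. That is a separate matter; it means that any loss of H1 power starts from above 80%.

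**Step 2: false H2-or-H3 claim when there is no effect.** For each outcome, z = (difference in proportions)/√(2·p̄(1−p̄)/n), chi-square = z², and the correlation between looks j<k is √(t_j/t_k). One outcome tested at |z|>1.96 three times has a 10.7% error. Two independent outcomes give 1 − (1 − 0.107)² = 20.3%; one final test of both gives 1 − 0.95² = 9.8%. Simulation of correlated paths gives:

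| Correlation of H2 and H3 statistics | Three looks at 0.05 | One final test |
|---|---|---|
| 0 | 20.3% | 9.8% |
| 0.5 | 18.8% | 9.1% |
| 0.8 | 16.3% | 7.8% |
| 0.9 | 14.7% | 7.0% |

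Counting claims of benefit only: 10.3% to 7.4% over three looks, 4.9% to 3.5% with one test.

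**Step 3: H1 power at a fixed sample, 33% against 15%.**

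Power = Φ{[0.18·√n − 1.96·√(2·0.24·0.76)] / √(0.33·0.67 + 0.15·0.85)}.

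At n = 50: (1.273 − 1.184)/0.590 = 0.15, so 56%. At n = 100: (1.800 − 1.184)/0.590 = 1.04, so 85%. At n = 150: 96%. Exact binomial enumeration gives 57%, 86% and 96%.

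**Step 4: H1 power when the written rule decides the stopping time.** Patient-level simulation, H1 at 33% against 15%, latent correlation 0 to 0.8:

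| H2 and H3 effect | Overall H1 power |
|---|---|
| 33% vs 15% | 62-72% |
| 33% vs 20% | 72-85% |
| 33% vs 25% | 83-93% |
| none | about 91-92% |

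In the first row, 72-82% of trials stop at look 1.

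**Step 5: the reported results.** The rounded percentages fit 6/54 vs 11/38, 7/54 vs 8/38 and 10/54 vs 12/38. Uncorrected chi-square on these counts gives 4.71, 1.07 and 2.09, as reported. For H2 (p=0.30) and H3 (p=0.15) the final data do not meet the stopping rule.

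**Step 6: an O'Brien-Fleming boundary at two-sided 0.05 per outcome.** False H2-or-H3 claim 9.7% to 7.1% over correlations 0 to 0.9, the same as one final test. In the least favourable row of step 4, H1 power is 82-90%.

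**The case against.** **Nothing in the report shows the rule did harm.** This stands. A reader might infer that the reported p=0.03 carries a 15-20% false-positive rate, or that the trial was stopped under this rule. The documents support neither. The rates concern H2 and H3; the p=0.03 belongs to a composite reported under H1; neither H2 nor H3 was claimed; and the Results do not say that a look occurred. If there was only one look, near 104 patients, the H2-or-H3 risk is the 7-10% of a single test.

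**The loss of H1 power is scenario-dependent.** This also stands. A reader might infer that the rule always takes H1 below 80%. It does so throughout the scenario where H2 and H3 share the 33% vs 15% effect, and in part of the range at 33% vs 20%. It does not at 33% vs 25% or with no effect. The plan gives 33% vs 15% for H1 only.

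**The hypotheses are directional.** H3, for example, states that infants "will experience a lower incidence of late or prolonged decelerations". Counting benefit only halves both rates, but the ratio of about two remains. The stopping rule itself names any difference, in either direction.

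**A continuity correction would lower the rates**, to about 12-14% against 6-8%. The plan specifies none, and the reported statistics are uncorrected.

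**Correcting across H2 and H3 goes further than the plan.** This is fair. The plan tests each hypothesis at 0.05, so the repair for repeated looks need not divide alpha between outcomes.

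**Conclusion.** The stopping rule is unsound as written. Over three looks the chance of a false H2-or-H3 claim is about 15-20% (correlation 0.9 to 0) instead of 7-10%; for benefit claims it is about 7-10% instead of 3.5-5%. A stop at the first look leaves H1 with about 57% power at the planned effect, and a stop at the second leaves 86%. Overall H1 power is anywhere from 62% to about 93%, according to H2 and H3 effects that the plan does not state.

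This rests on reading significant as p<0.05, on two-sided uncorrected chi-square tests and on equally spaced looks. If a stricter interim level was intended, the plan does not give it.

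For the report, the finding is one of disclosure: an unexplained end of enrolment near a planned look, and p-values with no statement on multiplicity.

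**What to change.** **(a) The plan, for any continued or repeated use.** In the Statistical Analysis section, replace the undefined significant difference with an O'Brien-Fleming boundary at two-sided 0.05 for each of H2 and H3: |z| > 3.471, 2.454 and 2.004 (p < about 0.0005, 0.014 and 0.045) at one third, two thirds and the end. If joint 5% control over H2 and H3 is wanted, use 0.025 per outcome instead (p < 0.00008, 0.0054 and 0.0231). At an assumed 33% vs 20%, power per outcome is 72.8% with one final test, about 72% with the first option and 61.7% with the second. Neither option controls error across H1, and neither should be applied to the existing data as if prespecified.

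**(b) The Results.** State whether and when interim looks took place, which outcomes were examined, and why enrolment ended at 104 consented of 300 planned.

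**(c) The p-values.** Label them as unadjusted for three hypotheses and for the planned looks.

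**(d) A separate reporting point.** Identify the result under Hypothesis 1 as a composite of RN or MD intervention for hypotension or late decelerations, and present it as nominal. Its counts imply 11.1% − 28.9% = −17.8 points, 95% Newcombe interval −34.7 to −1.5. Report planned H1, intervention for low blood pressure, on its own. The likely source is the form item "Did the anesthesia provider treat the maternal blood pressure during the 1 hour after epidural placement", but that mapping is an assumption and should be stated as one. Confirm that late decelerations under Hypothesis 3 means the form's single item covering late or prolonged; it may be shorthand.

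**Cost.** (b) to (d) need wording and one tabulation from an item already collected. (a) leaves the 300 maximum unchanged but gives up early stops. If all three outcomes are 33% vs 15%, the average total is about 193-203 patients (213-222 with the 0.025 option), against 120-132 under the written rule. At the reported pace of 104 consented in 31 months, about 3.35 a month, that is roughly 58-61 months instead of 36-39.

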## **Ethical Considerations**

- **Informed consent**

All study staff will complete CITI training. A study staff member will meet with potentially eligible patients and describe the study and answer any questions. If the patient is interested and meets all the inclusion/exclusion criteria, the study staff will review the *Informed Consent Form* and obtain written informed consent.

Patients will receive a copy of their signed Informed Consent form.

Informed Consent forms will be stored in a locked room that only staff will have access to. After the study closes, the signed Informed Consent forms will be boxed and sent to off-site storage and securely stored until the infant turns 21 years of age. At that time, the hard copy forms will be shredded.

- **Privacy information**

Personal identifiers will not be entered into the electronic database. Hard copy data collection forms and Informed Consent forms will be stored in a locked room that only staff will have access to. Electronic data will be stored on a password-protected folder on the U drive. Only study staff will have access to the electronic study documents. After data analysis and dissemination is completed, hard copy forms will be boxed and sent to off-site storage and securely stored until the infant turns 21 years of age. At that time, the hard copy forms will be shredded.

## Results

A randomized controlled trial was conducted with patients enrolled between October 29, 2022 and May 29, 2025. Patients were enrolled if they were at least 37 weeks gestation, laboring at Good Samaritan Hospital labor and delivery unit, planned to have epidural analgesia, and planned to have a vaginal delivery. They were excluded if they were under 18 years old, did not speak English, were unable to provide informed consent, attended less than 3 prenatal care office visits, were diagnosed with fetal demise, were diagnosed with fetal anomalies, had contraindications to both legs being elevated, had contraindications to receiving 1L of IV fluids, required IV hypertensive medications, or required IV magnesium.

A total of 104 patients were consented. Patients were randomized using a simple random number generator (1:1 randomization) into one of two study arms:

- Arm 1: Leg Elevation group (n=58)
- Arm 2: Standard Care group (n=44)
- 2 changed mind before randomization

Several patients in each arm were removed from the study before completion, resulting in **92 patients** who completed study:

- Arm 1: Leg Elevation group (n=58 consented - 4 removed = 54 completed study)
  - Delivered before epidural placed (1)
  - Had Category II tracings after consent signed and before epidural placed (2)
  - Breech and had c-section (1)
- Arm 2: Standard Care group (n=44 consented - 6 removed = 38 completed study)
  - Emergency c-section before epidural placement (1)
  - Had Category II tracings after consent signed and before epidural placed (3)
  - Didn't have 1L fluid bolus administered (2)

### Demographics:

	Leg Elevation Group n=54	Standard Care Group n=38	Comparison of Groups N=92
Age, years			
Mean (SD)	30.4 (4.4)	29.9 (4.2)	30.2 (4.3) No difference, t=0.55, p=0.291
Height			
Mean (SD)	65.1 (2.3)	65.6 (3.0)	65.3 (2.6) No difference, t=0.82, p=0.206
Weight			
Mean (SD)	198.2 (37.4)	195.6 (35.1)	197.1 (36.3) No difference, t=0.34, p=0.368

There's no significant difference between the two groups on age, height, weight, singleton or multiples, or number of previous pregnancies, number of previous births, number of living children, or number of previous abortions.

**Hypothesis 1:**

There is a significantly lower frequency of requiring RN or MD intervention for hypotension or late decelerations among patients in the intervention group (11%) compared to patients in the control group (29%),  $X^2 = 4.71$ ,  $p=0.03$ .

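### The result reported as Hypothesis 1 is an unplanned composite that adds responses to fetal decelerations; the planned and powered outcome, treatment of low blood pressure, is not reported.

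*Combined protocol and SAP*

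**What the plan says.** Three places in the combined protocol and SAP name the same Hypothesis 1 outcome.

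- **Hypothesis or Research Question.** Women in the leg-elevation arm "will experience a lower incidence of requiring intervention for low blood pressure compared to laboring women who receive epidural analgesia".
- **Research Plan, Sample Size Determination.** "A power analysis was conducted using a dichotomous outcome variable, requiring intervention for low blood pressure". The design rates are 33% falling to 15%.
- **Statistical Analysis, Hypothesis 1.** "a Chi Square test will be used to compare occurrence of receiving intervention for low blood pressure", at a significance level of 0.05.

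The form described under Data Collection has two separate yes/no items on staff action. One concerns the mother and reads "Did the anesthesia provider treat the maternal blood pressure during the 1 hour after epidural placement? Yes/No". The other concerns the fetal tracing: it records whether the nurse needed to act on late or prolonged decelerations over the same one-hour window.

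The Results entry headed Hypothesis 1 reports a "significantly lower frequency of requiring RN or MD intervention for hypotension or late decelerations among patients in the intervention group", at 11% versus 29%, chi-square 4.71, p=0.03. The Hypothesis 2 entry gives how often low blood pressure occurred (13% versus 21%, p=0.30). The Hypothesis 3 entry gives how often late decelerations occurred (19% versus 32%, p=0.15).

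**The concern.** The outcome under the Hypothesis 1 heading is not the one that was stated, powered and assigned a test. It joins treatment of the mother's blood pressure to a nursing response to the fetal tracing. Nothing in the plan defines that combination, and the Results do not mark it as a departure.

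It is also the only one of the three comparisons to cross 0.05, so the trial's sole positive claim rests on an outcome the plan does not contain. The composite is named in the sentence that reports it. Even so, because it sits under Hypothesis 1, 11% versus 29% can easily be taken as the planned effect on blood-pressure treatment, particularly beside design rates of 33% and 15%. The question the trial was sized to answer is left without a reported answer.

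**Working it through.** **1. Planned and reported outcomes side by side**

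| | Event counted |
|---|---|
| Hypothesis 1, power analysis, planned test | Intervention for low blood pressure |
| Results, Hypothesis 1 | Nurse or physician intervention for hypotension or late decelerations |
| Results, Hypothesis 2 | Occurrence of low blood pressure |
| Results, Hypothesis 3 | Occurrence of late decelerations |

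No row of the Results gives treatment of low blood pressure alone. Hypothesis 2 does not fill the gap, because it counts occurrence rather than treatment.

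**2. Reproducing the reported figures**

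The Results give 54 and 38 women completing the study. The only whole-number counts that round to 11% and 29% are 6/54 = 11.1% and 11/38 = 28.9%. The uncorrected chi-square for a 2x2 table is N(ad − bc)² / (product of the four margins):

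- Hypothesis 1: 92 × (6×27 − 48×11)² / (54×38×17×75) = 92 × 366² / 2,616,300 = 4.71, p=0.030. This matches.
- Hypothesis 2: 7/54 versus 8/38 gives 1.07, p=0.30. This matches.
- Hypothesis 3: 10/54 versus 12/38 gives 2.09, p=0.15. This matches.

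**3. Sensitivity of the composite to one event**

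- 7/54 versus 11/38: p=0.057.
- 6/54 versus 10/38: p=0.058.
- Reported counts with Yates correction: p=0.058. Fisher exact: p=0.054. The plan names only the chi-square test, so these two show fragility and nothing more.

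**4. What the composite implies for the planned outcome**

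Assumption: the composite counts a woman if either kind of intervention occurred, as its wording suggests. Blood-pressure treatment is then a subset, with a = 0 to 6 events out of 54 and b = 0 to 11 out of 38. That makes 7 × 12 = 84 possible pairs. The uncorrected chi-square gives p<0.05 in favour of leg elevation for 32 pairs and not for the other 52. The pairs are not equally likely, so this describes the range and is not a probability.

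| Leg elevation (of 54) | Standard care (of 38) | p |
|---|---|---|
| 5 | 11 | 0.014 |
| 3 | 8 | 0.024 |
| 5 | 10 | 0.029 |
| 4 | 8 | 0.056 |
| 6 | 10 | 0.058 |
| 3 | 6 | 0.10 |
| 5 | 8 | 0.11 |
| 6 | 8 | 0.19 |
| 3 | 5 | 0.20 |

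A further assumption, which the documents do not state, is that only women counted as hypotensive under Hypothesis 2 were treated. The standard-care count could then be at most 8, and p<0.05 would need 3 or fewer treated women in the leg-elevation arm.

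**5. Occurrence and intervention differ**

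In the leg-elevation arm 10 women had decelerations, but only 6 had any counted intervention, so at least 10 − 6 = 4 had decelerations without one. In standard care the figures are 12 and 11, so at least 1. This is not evidence of bias. It does show that the composite measures staff response as well as clinical events, in a trial where staff know the arm.

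**The case against.** The mismatch in wording is hard to dispute. The fair objections concern what is built on it.

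- **The plan never says that the anesthesia item is the Hypothesis 1 endpoint.** True: the hypothesis does not restrict who intervenes. It is, however, the only blood-pressure-treatment item listed for the form, so the mapping is a reasonable inference.
- **The upper limits of 6 and 11 depend on how the composite was built.** True, and the document does not define it. The limits follow from reading its wording literally and are conditional on that reading.
- **The planned result could be stronger than the composite.** True: 5 versus 11 gives p=0.014. The direction of change is unknown.
- **The non-significant results for Hypotheses 2 and 3 are not the composite's components.** True: they count occurrences, and the p-values for the two kinds of intervention are not given.
- **Knowledge of the arm affects blood-pressure treatment too.** True. Lack of blinding does not by itself separate the composite from the planned outcome.
- **Sensitivity to one woman is a small-sample feature.** True. It would also affect a correctly defined outcome with 92 women and does not show that the outcome was changed.

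None of these supplies the missing planned result or brings the composite into the plan.

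**Conclusion.** The concern holds. The outcome reported as Hypothesis 1 differs from the one the plan states, powers and tests, and the planned result is absent from the document. The only p-value below 0.05 among the three (0.030, on 6/54 versus 11/38) belongs to an undeclared composite, and one event either way moves it to about 0.057 or 0.058.

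This does not show that the planned comparison is non-significant. If the composite means either kind of intervention, the planned result could fall on either side of 0.05. As reported, the document supports no conclusion on Hypothesis 1. That changes what the trial can claim and needs correcting before the result is relied on.

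**What to change.** Under Hypothesis 1, report by arm the number and proportion of women whose form records that the anesthesia provider treated maternal blood pressure. Give the planned chi-square test, the risk difference and its 95% CI. State explicitly that this form item is the Hypothesis 1 endpoint.

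Move the composite to a separate line labelled post hoc and exploratory, define how it was built, and show its two components by arm. Remove it from the Hypothesis 1 conclusion.

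The cost is one re-tabulation of items already on the form, with no new data. The Hypothesis 1 result may become weaker or stronger, and the conclusion must follow whichever it is.

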**Hypothesis 2:**

There is no significant difference in frequency of low blood pressure among patients in the intervention group (13%) compared to patients in the control group (21%),  $X^2 = 1.07$ ,  $p=0.30$ .

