**Hypothesis 3:**

There is no significant difference in frequency of late decelerations among patients in the intervention group (19%) compared to patients in the control group (32%),  $X^2 = 2.09$ ,  $p=0.15$ .

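### The only significant result, Hypothesis 1, counts treatment decisions by non-blinded staff: it shows fewer interventions given, not fewer women needing them and not fewer events

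*Combined protocol and SAP*

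**What the plan says.** The Study Design section is open about masking: "This study will use a randomized, non-blinded, controlled design with two arms". Leg elevation on a ball is visible to anyone at the bedside.

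The plan for Hypothesis 1 is that "a Chi Square test will be used to compare occurrence of receiving intervention for low blood pressure", and the sample size was set on that outcome with "power of 0.8, and level of significance 0.05". The data collection form in the Research Plan has two items that record an intervention. The maternal item reads "Did the anesthesia provider treat the maternal blood pressure during the 1 hour after epidural placement? Yes/No". The fetal item, on what the nurse did about decelerations over the same period, reads "Did the RN have to perform any interventions to address prolonged or late decelerations during the 1 hour after epidural placement? Yes/No".

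The nurse completes the form. It also carries a threshold systolic pressure, but the plan does not tie treatment to that threshold and gives no other criterion for when staff intervene.

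The Results widen Hypothesis 1 to interventions by nurse or physician for either problem and report a "significantly lower frequency of requiring RN or MD intervention for hypotension or late decelerations among patients in the intervention group (11"%) against 29% in the control arm, p=0.03. For the events they report "no significant difference in frequency of low blood pressure among patients in the intervention group (13%) compared to patients in the control group (21"%), p=0.30, and "no significant difference in frequency of late decelerations among patients in the intervention group (19%) compared to patients in the control group (32"%), p=0.15.

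**The concern.** The Results describe Hypothesis 1 as the frequency of *requiring* intervention. What was recorded is whether intervention was given. In a non-blinded trial without a stated trigger, the two can differ by arm: staff may be readier, or less ready, to act when the legs are already raised.

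This matters because the Purpose of Study concerns fewer episodes of hypotension and fewer decelerations, and the interim stopping rule is also written on those two events. Neither differed significantly. A reader who meets one significant result and two non-significant ones, with no caveat, may take p=0.03 as evidence that leg elevation prevents the events.

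**Working it through.** **1. Recover the counts.** The Results print percentages only, with n=54 and n=38 analysed. One woman is 1.85 points in the first arm and 2.63 in the second, so only one count fits each rounded percentage.

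**2. Reproduce the printed tests.** With a and b the women with the outcome in the two arms, the uncorrected chi-square is

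X² = 92 × [a(38−b) − b(54−a)]² / [54 × 38 × (a+b) × (92−a−b)]

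| Outcome | Leg elevation | Standard care | X² | p | Printed |
|---|---|---|---|---|---|
| H1 intervention | 6/54 | 11/38 | 92×(162−528)²/(54×38×17×75) = 4.71 | 0.030 | 4.71, 0.03 |
| H2 low blood pressure | 7/54 | 8/38 | 92×(210−376)²/(54×38×15×77) = 1.07 | 0.301 | 1.07, 0.30 |
| H3 decelerations | 10/54 | 12/38 | 92×(260−528)²/(54×38×22×70) = 2.09 | 0.148 | 2.09, 0.15 |

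All three match.

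**3. Size and precision.** Risk differences, leg elevation minus standard care, with 95% intervals (difference ± 1.96 × √[p₁(1−p₁)/54 + p₂(1−p₂)/38]):

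- H1: −17.8 points (−34.5 to −1.2)
- H2: −8.1 points (−23.8 to 7.7)
- H3: −13.1 points (−31.1 to 5.0)

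All three point the same way and the intervals overlap widely.

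**4. Fragility of H1.** On the same counts, the Yates-corrected p is 0.058 and Fisher's exact p is 0.054. The plan names a chi-square test without mentioning a correction, so the uncorrected version is admissible. With one more intervention under leg elevation (7/54), X² = 92×(189−517)²/(54×38×18×74) = 3.62, p=0.057.

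**5. Interventions relative to events.** The overlap of hypotension and decelerations within women is not reported. The number of women with at least one event therefore lies between 10 (full overlap) and 10+7=17 (none) with leg elevation, and between 12 and 12+8=20 with standard care. Assuming that every intervention was in a woman with an event:

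- Leg elevation: 6/17=0.35 to 6/10=0.60
- Standard care: 11/20=0.55 to 11/12=0.92

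There are 8×9=72 combinations. The ratio is lower with leg elevation in 70 and higher in 2 (6/10 vs 11/19 or 11/20). Fisher p is below 0.05 in only 12. At the matched extremes it is 0.32 (6/17 vs 11/20) and 0.14 (6/10 vs 11/12).

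**The case against.** The strongest reply is that nothing was hidden. Intervention for low blood pressure was the planned and powered outcome, non-blinding is disclosed, and the Results themselves state that neither event differed significantly. No passage claims fewer events. H3 is also a yes/no item completed by the non-blinded nurse, so the weakness is not confined to H1. One p-value below 0.05 beside two above it does not show that H1 diverges from the events. All of this stands, and it is why the point is advisory. It does not remove the gap between intervention given and intervention required.

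A reader might go further and infer that the counts show staff holding back in the leg-elevation arm. The documents do not support that:

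- **Minimum figures.** At least 10−6=4 of 10 women with decelerations had no intervention under leg elevation, against at least 12−11=1 of 12 in control. These are lower bounds. If control-arm hypotension and decelerations did not overlap and all 8 hypotensive women were treated, only 11−8=3 interventions remain for the 12 women with decelerations, leaving 9 without.
- **Applying the control ratio.** 17×11/20=9.35 gives about 9/54, X²=1.98, p=0.16. This takes the control ratio as known and so assumes the bias it is meant to reveal. The fragility in step 4 reflects small numbers.
- **Other explanations.** Chance or milder events under leg elevation would give the same pattern. So could a hypotension measure taken after treatment: the listed form items include no hypotension item, and the only on-study pressure named is the next reading after the 40 minutes of positioning. The documents do not say what H2 was scored from.

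**Conclusion.** The point holds as a limit on interpretation. H1 shows that fewer interventions were given (6/54 vs 11/38), as decided and recorded by staff who knew the arm. It does not establish that fewer women needed intervention or that fewer events occurred.

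It would be equally wrong to infer that leg elevation had no effect on events. H2 and H3 both lean in its favour with wide intervals.

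The ratio of interventions to events is compatible with differing readiness to act but does not demonstrate it. That part rests on the assumption that every intervention was in a woman with a recorded event, and on an overlap the documents do not report. The recovered counts need only the printed percentages and group sizes. Severity: advisory.

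**What to change.** 1. Print the counts beside the percentages for all three hypotheses.
2. From the data already used to score H1–H3, tabulate by arm the event status (hypotension, deceleration, both, neither) against intervention, with anesthesia provider and nurse shown separately. State in a note which blood pressure reading defined hypotension. Keep the table descriptive: it conditions on an event after randomisation and the cells are small.
3. Reword the Hypothesis 1 result to say that fewer interventions were given, as decided by non-blinded staff, without a demonstrated reduction in hypotension or decelerations.

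The cost is one table and a revised sentence, with no new data collection. The downside is a less favourable headline.
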